APPENDIX V. SEMI-STRUCTURED INTERVIEW GUIDES

INTERVIEW GUIDE: KEY CLINICAL SITE STAFF

Interviewer: *Before you meet with the participant for the interview, be sure to look over answers from the Post-study Survey and the site's responses from the Site Feasibility Questionnaire about whether the site has indicated any specific initiative to achieve with the AIRQ™ or what made the site unique for participating in this study.*

Part 1. Before the interview begins, be sure to document verbal consent using the script below

Part 2. Below is the discussion guide, it is to be used as a guide only. The actual areas of conversation are fluid and may be discussed at moments different from the order appearing below.

PART 1. KEY CLINICAL SITE STAFF INFORMED VERBAL CONSENT SCRIPT

PART 2. INTERVIEW

INTERVIEW RULES FOR ALL INTERVIEWS

Please feel free to answer honestly. We are interested in your feedback and observations from implementing these tools in your clinical practice over the past several months.

Turn on Recorder and Begin Interview: This is [*interviewee's name*] with participant [*participant ID*] for Study EVA-26645-04 on [*Date*]. I want to confirm that you agree to participate in this interview and that you agree to today's interview being audio recorded. **Is that correct?**

Background

First, I would like to ask you some background questions.

1. What are your key responsibilities at the clinic?
2. What were your key responsibilities for this implementation study?
3. In general, how did your site conduct the patient visit? *Probe: by telehealth platform, by in-person clinic visit.?*
4. In general, how did your site conduct the telehealth visits? *Probe: by telephone, computer, tablet, etc.?*

Now I would like to ask you some questions about the process you used to administer the AIRQ™, the Asthma Checklist, and educational resources (PRECISION program) as part of a patient's telehealth visit for this study.

Process for Telehealth visit with AIRQ™

5. In your own words, how would you describe the process you used to administer the AIRQ™ to patients during a telehealth visit? (*listen for who administered AIRQ™ and how it was administered and process (i.e., as part of initial intake, by HCP, etc.)*)
6. Approximately how long did it take patients to complete just AIRQ™ during a telehealth visit?
7. Did patients have any problems completing the AIRQ™ as part of the telehealth visit?
 - a. Did they ask you questions about specific items included in the AIRQ™? If so, what type of questions did they generally ask?
8. What was the process you use to provide the AIRQ™ results to the HCP?

Process for In-Person visit with AIRQ™

9. In your own words, how would you describe the process you used to administer the AIRQ™ to patients during an in-person visit? (*listen for who administered AIRQ™ and how it was administered and process (i.e., as part of initial intake, by HCP, etc.)*)
10. Approximately how long did it take patients to complete just AIRQ™ during an in-person visit?
11. Did patients have any problems completing the AIRQ™ as part of the in-person visit?
12. Did any of your patients use the Spanish version of the AIRQ™? If so, how did you administer the Spanish version? Were there any difficulties using the Spanish version? Going back and forth between English and Spanish versions?
13. What was the process you use to provide the AIRQ™ results to the HCP?

Asthma Checklist and Educational Resources

14. Did you use the full Asthma Checklist and education resources from the study website? If so,
 - a. In what capacity did you use this information? (telehealth vs in-person)
 - b. What did you find most useful about this information?
 - c. What did you find least useful about this information?

Entire Program

15. Thinking about the entire PRECISION program, how much extra time at each patient telehealth visit did it take to incorporate the AIRQ™ as part of the telehealth visit? What about in-person visits?
16. Were there any specific steps or initiatives taken at your clinical site to implement the AIRQ™ for telehealth? Please explain.
17. What were some of the initial challenges of incorporating the PRECISION tools into your daily clinical practice? *Probe: implementing AIRQ™ on the telehealth platform and incorporating AIRQ™ to the regular in-person telehealth visit?*
18. How were you able to overcome these challenges?
19. What challenges remained throughout the study?
20. How can we address these challenges during future site trainings?
21. Which aspects of the PRECISION program are you most likely to continue using, and why? Which ones had the least value to your clinical practice/

Overall Comments

22. What did you think of the overall PRECISION program?
23. What do you think needs to be done to support the continued use of the PRECISION program at your clinical site?
24. Do you have any other comments or suggestions?

INTERVIEW GUIDE: CLINICIAN

Interviewer: *Before you meet with the participant for the interview, be sure to look over answers from the Post-study Survey and the site's responses from the Site Feasibility Questionnaire about whether the site has indicated any specific initiative to achieve with the AIRQ™ or what made the site unique for participating in this study.*

Part 1. Before the interview begins, be sure to document verbal consent using the script below

Part 2. Below is the discussion guide, it is to be used as a guide only. The actual areas of conversation are fluid and may be discussed at moments different from the order appearing below.

PART 1. CLINICIAN INFORMED VERBAL CONSENT SCRIPT

PART 2. INTERVIEW

INTERVIEW RULES FOR ALL INTERVIEWS

Please feel free to answer honestly. We are interested in your feedback and observations from implementing these tools in your clinical practice over the past several months.

Turn on Recorder and Begin Interview: This is [*interviewee's name*] with participant [*participant ID*] for Study EVA-26645-04 on [*Date*]. I want to confirm that you agree to participate in this interview and that you agree to today's interview being audio recorded. **Is that correct?**

Background

1. What are your overall thoughts on the AIRQ™, the Asthma Checklist, and educational resources (PRECISION program)? *Probe: Assess component, Review/Adjust component of Asthma checklist*
2. How useful was the AIRQ™ when used during a telehealth visit? *Probe: identify patients at risk, guide treatment, and asthma work-up and management?*
3. How useful was the AIRQ™ when used during an in-person visit? *Probe: identify patients at risk, guide treatment, and asthma work-up and management?*
4. Were there specific questions on the AIRQ™ that you thought were the most useful? The least useful?
5. How useful were the Asthma Checklist and other educational resources as part of the telehealth platform? In-person visit?
6. What did you like about the PRECISION program?
7. What did you not like about the PRECISION program?

Interviewer: Remind the clinician of any specific initiative they thought they could achieve with the AIRQ™, the Asthma Checklist, and educational resources (PRECISION program) or what made them unique for participating in this study before the interview.

1. When you started this study, you had indicated [specific QI initiatives/uniqueness of site]. Can you speak to this a bit? How has AIRQ™, the Asthma Checklist, and education resources (PRECISION program) been incorporated into this initiative? How has it helped? What were some of the challenges/benefits?
2. Will your site continue to incorporate the AIRQ™, Asthma Checklist, and educational resources (PRECISION program) when the study is over? Why or why not?
3. What do you think needs to be done to support the continued use of the PRECISION program in your clinical practice?

Do you have any other comments or suggestions?

Observational Study Protocol
Study Code D2287L00028 [EVA-26645-03]
Version 2.0
Date: June 16, 2022

CCI

Observational Study Protocol Form
Version 3.0
Form Doc ID: AZDoc0059948
Parent Doc ID: SOP LDMS_001_00164328

Observational Study Protocol
Study Code D2287L00028 [EVA-26645-03]
Version 2.0
Date June 16, 2022

APPENDIX BB. REMINDER E-MAILS FOR POST VISIT PATIENT SURVEY (ENGLISH VERSION)

Observational Study Protocol
Study Code D2287L00028 [EVA-26645-03]
Version 2.0
Date June 16, 2022

APPENDIX CC. REMINDER E-MAILS FOR POST VISIT PATIENT SURVEY (SPANISH VERSION)

Placeholder

APPENDIX DD. DESCRIPTION OF DRUGS IN EACH DRUG CLASS

MAINTENANCE PHARMACOLOGIC THERAPY	

ICS
 
 QVAR HFA 40 mcg (Beclomethasone)  Beclovent HFA 40 mcg (Beclomethasone)  Vanceril HFA 42 mcg (Beclomethasone)  QVAR HFA 80 mcg (Beclomethasone)  Beclovent HFA 80 mcg (Beclomethasone)  Vanceril HFA 84 mcg (Beclomethasone)  QVAR Redihaler 40 mcg (Beclomethasone)  QVAR Redihaler 80 mcg (Beclomethasone)  Pulmicort Flexhaler 90 mcg (Budesonide)  Pulmicort Flexhaler 180 mcg (Budesonide)  Pulmicort Respules 0.25 mg (Budesonide)  Pulmicort Respules 0.5 mg (Budesonide)  Pulmicort Respules 1 mg (Budesonide)  Aerospan HFA 80 mcg (Flunisolide)  Flunisolide  Flovent HFA 44 mcg (Fluticasone Propionate)  Flovent HFA 110 mcg (Fluticasone Propionate)  Flovent HFA 220 mcg (Fluticasone Propionate)  Flovent Disc 50 mcg (Fluticasone Propionate)  Flovent Disc 100 mcg (Fluticasone Propionate)  Flovent Disc 250 mcg (Fluticasone Propionate)  Azmanex Twisthaler 110 mcg (Mometasone)  Azmanex Twisthaler 220 mcg (Mometasone)  Azmanex HFA 100 mcg (Mometasone)  Azmanex HFA 220 mcg (Mometasone)  Arnuity Ellipta 100 mcg (Fluticasone Furoate)  Arnuity Ellipta 200 mcg (Fluticasone Furoate)  Triamcinolone Acetonide  Alvesco 80 mcg (Ciclesonide)  Alvesco 160 mcg (Ciclesonide)  Other (specify): _____  Other (specify): _____
 
ICS/LABA
 
 Advair Diskus 100/50 (Fluticasone/Salmeterol)  Advair Diskus 250/50 (Fluticasone/Salmeterol)  Advair Diskus 500/50 (Fluticasone/Salmeterol)  Advair HFA 45/21 (Fluticasone/Salmeterol)
	
LABA (Single inhaled medicine, not in a fixed-dose combination with an ICS or ICS/LAMA)
 
 Serevent/ Salmeterol  Foradil/Formoterol  Arcapta  Brovana  Indacaterol  Arformoterol  Striverdi/Olodaterol
 
LAMA
 
 Incuse Ellipta (Umeclidinium)  Spiriva Respimat 1.25 mcg (Tiotropium bromide)  Spiriva Handihaler (Tiotropium bromide inhalation powder)  Spiriva Respimat 2.5 mcg (Tiotropium bromide)  Tudorza/Aclidinium
 
Triple Therapy (fixed-dose combination)
 
 Trelegy Ellipta
 
LTRA
 
 Singulair 4 mg (Montelukast)  Singulair 5 mg (Montelukast)  Singulair 10 mg (Montelukast)  Accolate 10 mg (Zafirlukast)  Accolate 20 mg (Zafirlukast)  Zyflo 600 mg (Zileuton)
 
Theophylline Preparations
 
 Theo-24 100 mg (Theophylline)  Theo-24 200 mg (Theophylline)  Theo-24 400 mg (Theophylline)  Elixophylline 200 mg (Theophylline)  Elixophylline 300 mg (Theophylline)  Elixophylline 400 mg (Theophylline)  Theochron 100mg (Theophylline)  Theochron 200mg (Theophylline)  Theochron 300mg (Theophylline)  Theochron 400mg (Theophylline)
 
Chronic Add-on Therapy (Macrolides)
 
 Azithromycin (Zithromax)


MAINTENANCE PHARMACOLOGIC THERAPY	
 Advair HFA 115/21 (Fluticasone/Salmeterol)  Advair HFA 230/21 (Fluticasone/Salmeterol)  Wixela Inhub 100/50  Wixela Inhub 250/50  Wixela Inhub 500/50  Airelta Respclick 55/14 (Fluticasone/Salmeterol)  Airelta Respclick 133/14 (Fluticasone/Salmeterol)  Airelta Respclick 232/14 (Fluticasone/Salmeterol)  Breo Ellipta 100/25 (Fluticasone/Vilanterol)  Breo Ellipta 200/25 (Fluticasone/Vilanterol)  Dulera HFA 100/5 (Mometasone/Formoterol)  Dulera HFA 200/5 (Mometasone/Formoterol)  Symbicort 80/4.5 (Budesonide/Formoterol)  Symbicort 160/4.5 (Budesonide/Formoterol)	 Clarithromycin (Biaxin)  Erythromycin (Erythrocin) Biologics  Cinqair (reslizumab)  Dupixent (dupilumab)  Fasenra (benralizumab)  Nucala (mepolizumab)  Xolair (omalizumab)  Other: _____

1. OBJECTIVES

1.1 Primary Objectives

The goal of this project is to assess the process (ease of use and challenges to health care professionals [HCP] and patients) and potential benefits (ability to capture and take action to remediate previously unrecognized morbidity) of implementing the Asthma Impairment and Risk Questionnaire (AIRQ®), Asthma Checklist, and educational resources (PRECISION program) into clinical practice during telehealth and in-person visits.

This study is descriptive and there will be no formal hypothesis testing for the primary objective.

1.2 Secondary Objective

The secondary objectives of this study are:

1. To assess clinic visit experiences of patients with asthma and when the AIRQ®, Asthma Checklist, and educational resources (PRECISION program) are utilized as part of a telehealth or in-person visit with their HCP
2. To explore change in AIRQ® scores from the initial visit to follow-up visit(s) (when available)

1.3 Exploratory Objectives

Exploratory objectives include the following:

Additional exploratory analyses may occur to address additional clinically or psychometrically relevant questions of this sample.

2. STUDY DESIGN AND SAMPLE SIZE

This community program intervention study will examine the process of integrating the AIRQ®, Asthma Checklist, and educational resources (PRECISION program) into clinical practice using in-person or telehealth visits. Providers' use of patients' responses to the AIRQ®, Asthma Checklist, and educational resources to guide treatment and asthma work-up and management will be examined. All participants will be enrolled in the study by February 2022. Study duration for each site will be 12 months, including a nine month study implementation phase (starting when the last patient is enrolled at the site) and an additional three months of follow-up to assess the sustainability of using the PRECISION program in clinical practice (sustainability stage). The nine-month implementation stage will allow for potential follow-up visits for each enrolled patient. The three-month sustainability stage will allow for sites to continue to implement the PRECISION program in their clinical practice and for sites to describe any continued benefits of using the PRECISION program at their site.

Approximately 15 to 20 clinical sites will be recruited to participate in this study, categorized into the following practice clusters: (1) primary care site (e.g., private practice, FQHC; 2) specialty care site (pulmonary, asthma/immunology); and (3) novel sites (e.g., pharmacy, nurse practitioners, nurse educators, prescribers and non-prescribers, telehealth component of Allergy and Asthma Network).. Sites will be able to conduct in-person and telehealth visits for initial and follow-up visit(s).

During the clinic visit (telehealth or in-person), HCPs will assess the patients' responses to the AIRQ® questions, discuss the results with the patient, and use the Assess component of the Asthma Checklist (as appropriate per HCP judgment). Before completing the initial study visit, patients will be asked if they would be willing to complete additional questions and, for those who agree, sites will send them an electronic survey link (via YouGov) that will include the following questionnaires: the Asthma Clinic Experience (ACE) Questionnaire, [CCI](#)

Sociodemographic Questionnaire. If a follow-up visit (telehealth or in-person) is conducted during the follow-up period, the clinical site will administer the AIRQ® three-month recall version (regardless of timing of follow-up visit). Sites/HCPs will complete a Clinical Case Report Form (CRF) after the initial visit and after the first follow-up visit (if conducted) for each participant. For the initial and first follow-up visit for which patients complete an AIRQ®, HCPs will be required to review the Assess component of the Asthma Checklist and provide their responses on the CRF; while sites are encouraged to use the AIRQ® for any additional follow-up visits during the study and to provide documentation of the AIRQ® scores, additional CRFs will not be completed by the HCPs.

Additionally, Evidera will host a 30-minute conference call with each clinical site for up to four timepoints (touchpoints) to discuss the implementation of PRECISION tools (i.e., frequency of visits to and the number of portable document format (PDF) file views from study website), assess whether sites are meeting their targets for using the telehealth platform, address site questions, and discuss any challenges of implementing the PRECISION program. These meetings will take place at Months 1, 2, 3 (optional), and 6 and will be used to identify any sites that may benefit from participating in a re-training session. The optional Month 3 touchpoint will be based on whether the site has any difficulties with the study.

Study Population: Clinic staff will invite patients age ≥ 13 years with an HCP-confirmed asthma diagnosis who present for a clinic visit (telehealth or in-person) to complete the AIRQ® and participant questionnaires. Each site will aim to recruit approximately 50 to 75 patients with a total sample size ranging from approximately 750 to 1,500 patients. The number of patients recruited from each site may be modified (i.e., able to recruit > 75 patients) to ensure that the target study sample size is obtained.

Inclusion Criteria: Patients must meet all of the following criteria to be eligible for enrollment:

1. ≥ 13 years of age at the time of enrollment
2. Prior diagnosis of HCP-confirmed asthma
3. Able to read, understand, and speak English or Spanish sufficiently to self-complete or be administered the AIRQ™ via telephone, desktop computer, or mobile device (e.g., smartphone, iPad)
4. Provide consent (adults/parents/guardians) and assent (age 13 to 17 years) to participate in the study

Exclusion Criteria: Patients meeting any of the following criteria will not be included in the study:

1. Current diagnosis of active chronic obstructive pulmonary disease or any lower respiratory diagnosis other than asthma
2. Has a cognitive impairment, hearing difficulty, acute psychopathology, medical condition, or insufficient knowledge of the English or Spanish language that, in the opinion of the investigator, would interfere with their ability to agree to participate and/or complete the AIRQ™ or other study questionnaires.

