During the clinic visit (telehealth or in-person), HCPs will assess the patients' responses to the AIRQ™ questions, discuss the results with the patient, and use the Assess component of the Asthma Checklist (as appropriate per HCP judgment). Before completing the initial study visit, patients will be asked if they would be willing to complete additional questions and, for those who agree, sites will send them an electronic survey link (via YouGov) which will include the following questionnaires: the Asthma Clinic Experience (ACE) Questionnaire, **CCI** and a Patient

Sociodemographics Questionnaire. If a follow-up visit (telehealth or in-person) is conducted during the follow-up period, the clinical site will administer the AIRQ™ 3-month recall version (regardless of timing of follow-up visit). Sites/HCPs will complete a Clinical Case Report Form (CRF) after the initial visit and after the follow-up visit (if conducted) for each participant. It should be noted that for all visits (initial and follow up), HCPs will be required to review the Assess component of the Asthma Checklist and provide their responses on the CRF; the Adjust and Review components of the Asthma Checklist will be available, along with the other PRECISION resources, on the study website as well, but will not be mandatory to complete. **CCI**

Additionally, Evidera will host a 30-minute conference call with each clinical site for up to four (4) time points (touchpoints) to discuss the implementation of PRECISION tools (i.e., frequency of visits to and the number of PDF views from study website), assess whether sites are meeting their targets for using the telehealth platform, address site questions, and discuss any challenges of implementing the PRECISION program. These meetings will take place at Months 1, 2, 3 (optional), and 6 and will also be used to identify any sites that may benefit from participating in a re-training session. The optional Month 3 touchpoint will be based on whether the site is having any difficulties with the study.

Study Population: Clinic staff will invite patients age ≥ 13 years with HCP-confirmed asthma diagnosis who are presenting for a clinic visit (telehealth or in-person) to complete the AIRQ™ and participant questionnaires. Each site will aim to recruit approximately 50 patients with a total sample size ranging from approximately 750 to 1,500 patients.

Inclusions Criteria:

Patients must meet all of the following criteria to be eligible for enrollment:

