APPENDIX G. AIRQ™ 3-MONTH RECALL (ENGLISH VERSION)

Evidera 138 Evidera Page 1 of 1

Participant ID Verification Code Date 20 DD MMM YYYY

Asthma Impairment and Risk Questionnaire (AIRQ™)

For use by health care providers with their patients 12 years and older who have been diagnosed with asthma. AIRQ™ is intended to be part of an asthma clinic visit.

Please answer all of the questions below.

In the past 2 weeks, has coughing, wheezing, shortness of breath, or chest tightness:

1. Bothered you during the day on **more than 4 days**? Yes No
2. Woke you up from sleep **more than 1 time**? Yes No
3. Limited the activities you want to do **every day**? Yes No
4. Caused you to use your rescue inhaler or nebulizer **every day**? Yes No

Please see all prescribing information for all products.

In the past 2 weeks:

5. Did you have to limit your social activities (such as visiting with friends/relatives or playing with pets/children) because of your asthma? Yes No
6. Did coughing, wheezing, shortness of breath, or chest tightness limit your ability to exercise? Yes No
7. Did you feel that it was difficult to control your asthma? Yes No

[figure not shown]
In the past 3 months, has coughing, wheezing, shortness of breath, or chest tightness:

8. Caused you to take steroid pills or shots, such as prednisone or Medrol®*? Yes No
9. Caused you to go to the emergency room or have unplanned visits to a health care provider? Yes No
10. Caused you to stay in the hospital overnight? Yes No

Total YES Answers

What Does My AIRQ™ Score Mean?

The AIRQ™ is meant to help your health care providers talk with you about your asthma control. The AIRQ™ does not diagnose asthma. Whatever your AIRQ™ score (total YES answers), it is important for your health care team to discuss the number and answers to each of the questions with you. All patients with asthma, even those who may be well-controlled, can have an asthma attack. As asthma control worsens, the chance of an asthma attack increases. Only your medical provider can decide how best to assess and treat your asthma.

*Medrol® (Pfizer, Inc.) or methylprednisolone. The trademarks depicted above are the property of their respective owners.

[figure not shown]
Global Strategy for Asthma Management and Prevention: ©2020 Global Initiative for Asthma

AIRQ™ is a trademark of AstraZeneca.

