Asthma Action Plan ^{1,2,4}	Appropriate use of rescue and maintenance therapies	 Adjust current level of therapy  Continue current therapy	
Inhaler Technique ^{1,2,4}	When and how to use an asthma action plan	 Develop or update asthma action plan	
Psychological Issues ^{1,2}	Proper technique for use of inhaler devices	 DPI education  Nebulizer education  pMDI education  Soft Mist education	Review at next visit?  Y  N  Review at next visit?  Y  N  Review at next visit?  Y  N  Review at next visit?  Y  N
Spirometry ^{1,2,4}	Role of depression and anxiety in asthma	 Refer for counseling	
Tobacco Use ^{1,2,5}	Spirometry for diagnosis and management of asthma	 Spirometry  Spirometry: Pre-/post-bronchodilator	
Vaccinations ^{1,2,6,7}	Active and passive tobacco smoke exposure	 Tobacco cessation counseling/pharmacotherapy	
Influenza virus Pneumococcal pneumonia		 Influenza vaccine  Pneumococcal vaccine	

Review Response: Schedule a visit to review your patient's response to the selected ADJUST items above. Review topics can include: symptoms, exacerbations, side effects, lung function, and patient (and parent) satisfaction. Timing of the review visit (2 weeks to 6 months) depends on clinical urgency and what changes to treatment have been made.¹²

Regardless of level of asthma control, consider referral to an asthma specialty center if your patient has, for example, a history of near fatal asthma, confirmed food allergies or anaphylaxis, aspirin-exacerbated respiratory disease (AERD), allergic bronchopulmonary aspergillosis (ABPA), occupational asthma, or ≥2 systemic steroid bursts in a year.¹³

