4.1.3.1 AIRQ®

The AIRQ® includes 10 questions concerning patient medication use, asthma symptoms, medical visits, and tests. All response options are in yes/no format with a two-week recall for symptom-based impairment questions (items 1–7) and 12-month recall for exacerbation-based risk questions (items 8–10). The AIRQ® was developed iteratively, and a targeted review of research articles, current asthma guidelines and screeners, grey literature, and a secondary analysis of qualitative patient data informed the initial development of the AIRQ®. Five clinical experts, representing primary care and specialty care (including an allergist/immunologist, two pulmonologists, a nurse PhD researcher, and a family practitioner), academic and community practices, and five geographic regions of the United States (US), participated in five web-based focus groups to further develop the AIRQ®. The AIRQ® was subsequently presented at six advisory board meetings, in which more than 141 clinical experts, practitioners, asthma educators, and patient advocates reviewed and provided additional suggestions for refinement. All participants will complete the AIRQ® at their initial visit, whether in-person or via telehealth. Scoring information is located in Appendix A.

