AIRQ® score and control level at the initial visit and Follow-up AIRQ® score and control level at follow-up visit(s) will be explored overall and by practice cluster, and presented using descriptive statistics (n, frequency, mean, SD) (Table 4a, Table 10a and Table 10j). The change in AIRQ® between initial visit and first follow-up visit will be evaluated using paired t-tests for the overall sample, and by practice cluster (Table 15). If the sample size allows, change in AIRQ® score will also be evaluated based on elapsed time from initial visit to follow-up by groups (e.g., 0–3 months; 4–6 months; 7–9 months). In Table 16, shift analyses will be conducted to evaluate change in AIRQ® control score between the initial and first follow-up visit. The frequency of patients improving, maintaining or worsening in AIRQ® control level from initial to first follow-up visit will be described in Table 17. Similarly, shift analyses for AIRQ® control score between the initial and final follow-up visit will be presented in Table 18, and the frequency of patients improving, maintaining or worsening in AIRQ® control level from initial to final follow-up visit will be described in Table 19. If the sample size for additional AIRQ® completions after the first follow-up allows, an additional exploratory analysis will be to explore the trajectory of change in AIRQ® score in relation to visit number and other clinical variables.

Statistical analysis plan
D2287L00028 (EVA-26645)

AstraZeneca
27 Sep 2023

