Appendix A. Scoring Information

AIRQ®

The AIRQ® includes 10 questions with Yes/No responses. A total AIRQ® score is generated by summing the number of “Yes” responses. The scores for the AIRQ® range from 0–10. Patients with scores of 0 or 1 are considered “well-controlled,” patients with scores of 2–4 are considered “not well-controlled,” and patients with scores of 5–10 are considered “very poorly controlled.”

ACE

There are eight questions on the ACE with Likert scale responses (Strongly Agree, Agree, Disagree, Strongly Disagree), and one open-ended question. There is no total score for the ACE. Scores for each individual item will be described by frequency.

NAEPP Step Coding

Code	Maintenance Therapy	Rescue therapy
Step 1	No daily medication checked	SABA alone with no maintenance therapy ^a
Step 2	Low-dose ICS	SABA with maintenance therapy ^b
	Theophylline Preparations	
	Leukotriene modifier	
	No daily medication checked	ICS+ SABA as rescue therapy alone Fixed dose combination fast-acting LABA/ICS alone as rescue
Step 3	Medium/High-dose ICS	For Steps 3 through 6, step assignment is based on maintenance therapy only.
	Low-dose ICS + LAMA	
	Low-dose ICS+ leukotriene modifier	
	Low-dose ICS + theophylline preparation	
	Low dose ICS + LABA	
Step 4	Medium-dose ICS/LABA	
	Medium dose ICS + LAMA	
	Medium/high dose ICS + theophylline	
	Medium/high dose ICS + leukotriene modifier	
Step 5	High-dose ICS/LABA + LAMA	
	High-dose ICS/LABA	
Step 6 ^c	Any maintenance therapy AND	Chronic oral systemic corticosteroids OR Biologic

^a Possible alternative: “SABA as rescue therapy via nebulizer without other rescue or maintenance therapies” or “Primatene Mist as rescue and no maintenance therapy”

^b Possible Alternative: “SABA as rescue therapy via nebulizer with other rescue maintenance therapies” or “Primatene Mist as rescue with maintenance therapy(s)”

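### At follow-ups under about three months, AIRQ items 8–10 look back past the initial visit, so early and later change scores are not comparable if event rates changed around that visit

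*SAP*

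**What the plan says.** SAP section 2 fixes the follow-up instrument whatever the interval: "the clinical site will administer the AIRQ® three-month recall version (regardless of timing of follow-up visit"). The protocol synopsis has the same rule: "the clinical site will administer the AIRQ™ 3-month recall version". Protocol Appendix G words the stem of items 8–10 as "In the past 3 months, has coughing, wheezing, shortness of breath, or chest tightness", so the window runs back from the follow-up date and not from the initial visit.

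The initial form has a "12-month recall for exacerbation-based risk questions (items 8–10") and a "two-week recall for symptom-based impairment questions (items 1–7"). The two-week window is the same on the follow-up form. SAP Appendix A gives the scoring: "A total AIRQ® score is generated by summing the number of “Yes” responses". The range is 0–10, with control levels cut at 0–1, 2–4 and 5–10.

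The follow-up analysis set (SAP section 3) has no minimum interval. The Asthma Checklist in Protocol Appendix K says "Timing of the review visit (2 weeks to 6 months) depends on clinical urgency".

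SAP 5.1.2 plans paired t-tests of change to first follow-up, overall and by cluster (Table 15), and control-level shifts (Tables 16–17). If the sample size allows, "change in AIRQ® score will also be evaluated based on elapsed time from initial visit to follow-up by groups", with 0–3, 4–6 and 7–9 months as example groups. SAP 6.1 covers optional survey response and the selection of more severe patients into follow-up. It does not mention the recall window.

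**The concern.** Take a patient who had a steroid course three weeks before the initial visit, returns at four weeks and has had no event since. Item 8 is Yes at both visits. The same patient returning at four months answers No. The scores differ because of the return date, not because of anything that happened after the program began.

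Change in AIRQ is a named secondary objective. One point can move a patient across a control boundary (1 to 2, or 4 to 5), so one carried-over Yes can hide an improvement in the shift tables. Timing also differs between clusters by design: primary care and specialty sites use the first follow-up, while novel coaching sites complete the follow-up form at the final session. The amount of overlap may therefore differ between the clusters that Table 15 sets side by side.

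**Working it through.** The plan gives no figure for this effect, so there is none to reproduce. Inputs from the documents are the three-month window at follow-up, the 12-month window at the initial visit, three Yes/No items and no minimum interval. Everything about event rates and visit timing below is assumed.

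**Overlap.** For a follow-up t days after the initial visit, the share of the window that falls before that visit is max(0, 91 − t)/91.
- 14 days: 77/91 = 85%
- 28 days: 63/91 = 69%
- 60 days: 31/91 = 34%
- 91 days or later: 0%

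If visits are spread evenly from 2 weeks to 3 months, the average overlap in the 0–3 month group is 42%. If they are spread evenly from day 0, it is 50%. In the 4–6 and 7–9 month groups it is zero.

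**Effect on the score.** For each item, P(Yes) = 1 − exp(−expected events in the window), summed over items 8–10. Assumed yearly rates for items 8/9/10 are low 0.4/0.3/0.03, mid 0.7/0.6/0.06 and high 1.2/1.0/0.15.

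Worked case, mid rates, rates halving on the day of the visit:
- Three-month window at the old rates: exponents 0.175, 0.15, 0.015 give 0.161 + 0.139 + 0.015 = 0.315.
- Follow-up at 1 month (2 months at the old rate, 1 at half): exponents 0.1458, 0.125, 0.0125 give 0.136 + 0.118 + 0.012 = 0.266.
- Follow-up at 3 months or later: exponents 0.0875, 0.075, 0.0075 give 0.084 + 0.072 + 0.007 = 0.164 (unrounded sum).
- Average over 2 weeks to 3 months: 0.228. Gap between early and later groups: 0.228 − 0.164 = 0.064.

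The same calculation gives these gaps (0–3 month group minus later groups, in points of the 0–10 score, visits even from 2 weeks):

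| Scenario | Low | Mid | High |
|---|---|---|---|
| Constant rate, no effect | 0.00 | 0.00 | 0.00 |
| Rate × 0.7 after the visit | 0.02 | 0.04 | 0.06 |
| Rate × 0.5 after the visit | 0.04 | 0.06 | 0.10 |
| No effect; rate × 2 in the 3 months before | 0.07 | 0.12 | 0.18 |
| No effect; rate × 3 in the 3 months before | 0.13 | 0.22 | 0.33 |

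Spreading visits from day 0 raises the largest gap to 0.385. The gap between 4–6 and 7–9 months is 0.00 in every row.

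**For scale.** With constant rates and no effect, the change from 12-month to 3-month recall alone lowers the items 8–10 score. At mid rates the fall is 1.013 − 0.315 = 0.70, and across the rate sets it is 0.44 to 0.95. It is the same in all three time groups, so it is a different problem from this one.

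**The case against.** The strongest reply is that overlap alone does nothing. The window is always three months long, so with a constant event rate the expected score is the same at every follow-up time. That is correct. A reader might infer that the form by itself creates a trend over the three time groups. The documents do not support this: a gap needs rates that differ before and after the visit, and it is then one step at three months, with nothing between the two later groups.

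A reader might also infer that early follow-ups cannot show benefit. Take one item whose rate halves from 1.0 to 0.5 per year. On a three-month window P(Yes) falls from 22.1% to 11.7% once overlap has passed, but only to 20.6% at 2 weeks and 19.0% at 4 weeks. That is 15% and 29% of the change. This takes a three-month baseline, however, and the study's baseline is 12 months, where P(Yes) is 1 − exp(−1) = 63.2%. The recorded fall would be 42.7 percentage points at 2 weeks against 51.5 from 91 days. Early change would be recorded, mostly because of the recall mismatch.

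Other points also stand. The items are Yes/No, so an old event matters only if no newer one occurred. The elapsed-time analysis is conditional, its groups are examples, and no trend or between-group test is specified. The documents hold no visit-timing data. The 2-week to 6-month range comes from checklist pages that Protocol 4.1.7 makes optional, so it shows that early visits are foreseen but not how many occur.

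What survives is that the condition is not remote. A fall in event rate is the benefit that the change analysis would look for, and patients enrol when presenting for a visit. The pooled t-tests and shifts are not conditional on sample size.

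**Conclusion.** The point holds in conditional form. For follow-ups under about three months, items 8–10 include pre-visit time, and nothing in the plan prevents, adjusts for or mentions this. If event rates changed around the initial visit, the 0–3 month group is not comparable with later groups, and Tables 15–17 depend partly on return time.

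The size is modest: about 0.02 to 0.10 points if rates fall by 30% to 50%, and 0.07 to 0.33 if there is no effect but rates were two to three times higher in the three months before the visit. These figures depend on the assumed rates and on evenly spread visits from 2 weeks. Items 1–7 are unaffected at any follow-up beyond two weeks. This is a limited bias in a secondary outcome, worth correcting because the data to do so are already collected.

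**What to change.** In SAP 5.1.2:

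- Keep the planned total-score and shift analyses. Control levels exist only on the ten-item total, so dropping the total for early returners would lose too much.
- Split the elapsed-time groups at 91 days, so that the first group is exactly the overlapping visits.
- Report change on items 1–7 separately from items 8–10, overall and by elapsed-time group. Protocol 5.1.2 already plans change by item; the SAP does not carry this over.
- Repeat Tables 15–17 in follow-ups at 91 days or later as a sensitivity analysis. In the model above this removes the overlap gap in every scenario.
- For earlier visits, describe events from Follow-up CRF item 8 per time at risk since the initial visit. That item asks about the time since the last visit, so check at coaching sites that this means the initial visit. SAP Appendix B reports no medical record history for the novel site, so this description may be limited to the other clusters.

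In SAP 6.1, state that items 8–10 in follow-ups under 91 days include pre-visit time.

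The cost is some extra tables and a date filter on visit dates that both CRFs already record. The sensitivity sample will be smaller and selected on return time, and its totals will still carry the 12-month versus 3-month mismatch, which needs its own remedy. SAP Appendix B describes analyses already run, so these additions should be labelled as made afterwards.
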